8.5.1 Additional Analyses of Primary Endpoint

The below additional analyses (identified as sensitivity analyses in tables) described below may be performed for the primary efficacy endpoint, SSC:

- The primary analysis will be repeated using the actual revision type.
- A CMH test for SSCs stratified by randomized and actual revision type for the ITT, PP, and mPP will be included. Odds ratios and 95% confidence intervals will be presented.
- Summary of SSC events by type which include superficial SSI, deep SSI, dehiscence, seroma, hematoma, skin necrosis, or continued drainage based on the ITT, mITT, PP, and mPP analysis sets. Additionally, we will include SSC events of continued drainage that developed into SSIs.
- Summarize SSC events required intervention by type which include superficial SSI, deep SSI, dehiscence, seroma, hematoma, skin necrosis, and continued drainage based on the ITT, mITT, PP, and mPP analysis sets.
- For the septic and aseptic subpopulations, a Chi-square or Fisher's test as appropriate, will be performed within each actual revision type for SSC incidence rates between treatment groups based on the corresponding septic and aseptic mITT analysis sets.
- Perform a Fisher's exact test or Chi-square to compare the SSC incidence rates between two treatment arms without revision type stratification based on the mITT analysis.
- Multivariable analyses comparing the treatment groups with covariate adjustment where possible covariates might include (but not limited to) site, age, BMI, sex, type of revision (aseptic or septic), and subject comorbidities using logistic regression based on the mITT.

- Analyses comparing the heterogeneity of the treatment groups across clinical sites using logistic regression. (CMH) test stratified by clinical site based on the mITT.

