4 STUDY ENDPOINTS

4.1 Primary Endpoint

The primary endpoint is the subject incidence of Investigator-assessed surgical site complications (SSCs) within 90 days of TKA revision in subjects treated with ciNPT as compared to standard of care (SOC) surgical dressing. SSCs include any occurrence of superficial surgical site infection (SSI), deep SSI, dehiscence, seroma, hematoma, skin necrosis, or continued drainage as outlined in Section 4.11.1 of the study protocol. Three possible values for the primary endpoint are:

- “Occurred”: If the subject had one or more occurrences of SSC on or before 90 days post TKA revision;
- “No occurrences”: If the subject had an assessment of SSC on or after 90 days post TKA revision and had no known occurrence of any SSC within 90 days of the TKA revision.
- “Incomplete follow-up”: If the subject had no known occurrences of SSC and did not have any SSC assessment at least 90 days post TKA revision.

The start date of the complication will be recorded in order to calculate the number of days from the revision surgery until occurrence of the event.

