5 ANALYSIS SETS

The following analysis sets are planned for this study:

- Safety Analysis Set: The Safety Analysis Set consists of all randomized subjects who received any study-related treatment procedures. Subjects will be analyzed according to the study treatment they received immediately following the TKA revision.
- ITT Analysis Set: The ITT (intention-to-treat) Analysis Set consists of all randomized subjects. Subjects will be analyzed according to their randomized treatment assignment.
- mITT Analysis Set: The modified ITT Analysis Set will include subjects in the ITT analysis set with the following: 1) who had any SSC on or before 90 days post TKA revision, or 2) had an assessment of SSC on or after 90 days post TKA revision and had no known occurrence of any SSC within 90 days post the TKA revision. Subjects will be analyzed according to their randomized treatment assignment.
- Per-Protocol Analysis Set: This will include subjects in the mITT analysis set who had no disqualifying protocol deviation(s) that would impact the interpretation of the primary endpoint. The disqualifying protocol deviation(s) for exclusion from this set will be defined and documented in a treatment-blinded fashion prior to the final database lock by the Protocol Deviation Review Committee. Subjects will be analyzed according to their randomized treatment assignment.
- Modified Per-Protocol (mPP) Analysis Set: This will include subjects in the Per-Protocol analysis set excluding any subjects who received prohibited therapy as described in Section 4.15 of the study protocol or any subjects that received alternative therapy following the study treatment period.

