7 GENERAL STATISTICAL CONSIDERATIONS

7.1 General Considerations

- Data processing, tabulation of descriptive statistics, calculation of inferential statistics, and graphical representations will be performed primarily using SAS (release 9.4 or higher). If the use of other software is warranted, the final statistical report will detail software deployed along with their reasons for use.
- Summaries of continuous variables will show the number of non-missing values [n], along with the mean, median, standard deviation, minimum and maximum. In general, the maximum and minimum values will be presented to the same precision as the raw data; the mean and median will be presented to one decimal place more than the raw data. The standard deviation and confidence interval limits will be presented to two decimal places more than the raw data.
- P-values will be presented to four decimal places. A p-value less than 0.0001 will be presented as < 0.0001 or $< .0001$.
- The most recent assessment prior to TKA revision procedure will be used as the baseline reference for all analyses which incorporate a baseline value.
- Change from baseline will be calculated using the relevant post initial dressing application of either ciNPT or SOC value minus baseline value. Percent change from baseline will be calculated using change from baseline value divided by baseline value and multiplied by 100.

- Summaries of categorical (qualitative) variables will include the frequency and percentage of subjects. In general, the denominator for the percentage calculation will be based upon the total number of subjects in the study population, unless otherwise specified. Percentages will be presented to 1 decimal place unless otherwise specified.
- Other ad hoc data analyses to characterize the activity of the treatment may be conducted. These additional ad hoc analyses will be decided at the time of analysis. Ad hoc analyses will be identified in the output and the CSR and labeled as such.
- All collected data will be listed for all subjects who provided informed consent.
- For all exploratory endpoints, assessments performed outside the scheduled visit windows may not be included in the analysis but will be listed separately.

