7.3 Handling of Missing data/Dropouts

In general, missing data will not be imputed except for the followings:

- the date of AEs as described in Section 7.2 of this document

- the data imputation for sensitivity analyses for exploratory endpoints Pain, KOOS scores and PROMIS Global 10 as described in Sections 8.7.1, 8.7.2 and 8.7.3 respectively

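### The ITT CMH test in SAP 8.5.1 either repeats the mITT result or treats subjects lost without a recorded SSC as event-free, so it does not test whether missing 90-day outcomes matter

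*SAP*

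**What the plan says.** SAP 8.5.1 lists optional additional analyses of SSC, to be labelled as sensitivity analyses in the tables. One of them reads: "A CMH test for SSCs stratified by randomized and actual revision type for the ITT, PP, and mPP will be included". Odds ratios with 95% intervals are to accompany it.

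The sets are defined in SAP 5. "The ITT (intention-to-treat) Analysis Set consists of all randomized subjects". The mITT set keeps ITT subjects who had an SSC by day 90, or who "had an assessment of SSC on or after 90 days post TKA revision and had no known occurrence of any SSC within 90 days". Both per-protocol sets are drawn from mITT.

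SAP 4.1 gives the primary endpoint three values. The third, Incomplete follow-up, applies as follows: "If the subject had no known occurrences of SSC and did not have any SSC assessment at least 90 days post TKA revision".

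On missing data, SAP 7.3 says: "In general, missing data will not be imputed except for the followings". The exceptions are adverse event dates and "the data imputation for sensitivity analyses for exploratory endpoints Pain, KOOS scores and PROMIS Global 10". SSC is not among them.

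On summaries of categorical variables, SAP 7.1 says that, unless otherwise specified, "the denominator for the percentage calculation will be based upon the total number of subjects in the study population".

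**The concern.** A CMH test of SSC needs a two-level outcome. The only subjects who separate ITT from mITT are those with no outcome value, and the SAP neither assigns them one nor allows one to be imputed. The ITT test therefore cannot do what its label suggests.

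Agreement between the ITT and mITT tests could be read as evidence that missing 90-day outcomes do not matter, when it follows from how the sets are built or from an undeclared assumption. The question is a real one in this trial. It is open-label and expects 5%-10% loss against a targeted difference of 10 percentage points. Protocol 4.15 requires withdrawal after further surgery through the incision, or after cross-over therapy in the absence of an SSC. Protocol 4.4.2 collects no data after withdrawal. Loss may therefore depend on outcome or on arm.

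**Working it through.** **The plan's own figures.** For 20% v 10%, two-sided 0.05 and 80% power:

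n = [1.960 × √(2 × 0.15 × 0.85) + 0.842 × √(0.20 × 0.80 + 0.10 × 0.90)]² / 0.10² = [0.990 + 0.421]² / 0.01 ≈ 199 per arm.

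This matches SAP 2.1 (398 evaluable). With 440 randomized, the allowance for loss is 440 − 398 = 42, or 9.5%.

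**Set algebra.** ITT minus mITT is the group with no SSC recorded and no assessment at or after day 90, which is exactly Incomplete follow-up. Without imputation there are two forms:
1. Drop them. The ITT table is then the mITT table.
2. Keep them in the denominator as not 'Occurred'.

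The identity in form 1 is like for like. By randomized revision type it equals the primary test. By actual type it equals the mITT repeat in the first bullet of SAP 8.5.1.

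**Illustrative tables (assumed).** 220 per arm, 110 per stratum, 21 lost per arm (11 septic, 10 aseptic). The statistic is Q = [Σ(a − E)]² / ΣV over strata, with E and V the usual hypergeometric mean and variance and no continuity correction. The final threshold is 0.048.

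Table B, borderline effect: SSCs 21/99 v 33/99 septic and 4/100 v 7/100 aseptic (ciNPT v SOC).
- mITT, and ITT form 1: Σ(a − E) = (21 − 27) + (4 − 5.5) = −7.5; ΣV = 9.868 + 2.612 = 12.480; Q = 56.25 / 12.480 = 4.507.
- ITT form 2: the numerator is unchanged; ΣV = 10.233 + 2.624 = 12.857; Q = 4.375.

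Table A, near the design effect, has 16/99 v 33/99 and 3/100 v 7/100.

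| Handling of the 42 lost | A: p (OR) | B: p (OR) |
|---|---|---|
| mITT | 0.0021 (0.391) | 0.0338 (0.542) |
| ITT form 1, dropped | 0.0021 (0.391) | 0.0338 (0.542) |
| ITT form 2, event-free | 0.0024 (0.400) | 0.0365 (0.552) |
| All scored as SSC, both arms | 0.0149 (0.564) | 0.0868 (0.674) |

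Tipping point, with lost SOC subjects kept event-free and SSCs added among lost septic ciNPT subjects: significance is lost at 7 added SSCs in A (p = 0.0511) and at 1 in B (p = 0.0521). Neither form of the planned ITT test would reveal that difference in fragility.

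**Unequal loss, form 2.** mITT rates are held at 21.5% v 33% septic and 4.5% v 6.9% aseptic (mITT p 0.051 to 0.053), with 42 lost in total.

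| Lost ciNPT:SOC | ITT form 2 p |
|---|---|
| 31:11 | 0.018 |
| 26:16 | 0.032 |
| 21:21 | 0.055 |
| 16:26 | 0.090 |
| 11:31 | 0.142 |

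The 31:11 split is 14.1% v 5.0% by arm. It is within the planned total, but one arm is above 10%.

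**Effect of timing.** Suppose the true risk is 20% in both arms and loss is 5% SOC v 10% ciNPT.
- All losses before any event: form 2 shows 0.20 × 0.95 = 19.0% v 0.20 × 0.90 = 18.0%, a false 1-point benefit. The mITT shows 20% v 20%.
- All events before any loss: form 2 shows 20% v 20%. The mITT shows 0.20 / (0.20 + 0.80 × 0.95) = 20.8% v 0.20 / (0.20 + 0.80 × 0.90) = 21.7%, because it keeps lost subjects who had events and drops those who did not.

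**The case against.** Several points on the other side stand.

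- A reader might infer that every lost subject is counted as complication-free. That is wrong: a subject with an SSC before loss is 'Occurred' and belongs to mITT. Only those lost without a recorded SSC are affected.
- The event-free form has weak textual support. The SAP 7.1 denominator rule governs percentages in summaries, not the coding of a test outcome. SAP 4.1 requires a day-90 assessment for 'No occurrences', and SAP 8.5 tabulates Incomplete follow-up as its own category. That favours the drop-out form, which is redundant but adds no bias to mITT.
- A reader might infer that agreement in ITT would be meaningless. That is too strong. Form 2 can differ from mITT, is stricter when SOC loses more, and is the less biased of the two if events precede losses.
- The analysis is optional. The superiority claim rests on the mITT tests, and losses are disclosed by arm and by reason for exclusion (SAP 8.1, 8.5).
- SAP 8.7.6 plans Kaplan-Meier curves and a log-rank test with censoring, on ITT by the default in SAP 8.7. This does use partial follow-up.

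These points limit the consequence but do not remove the gap. The time-to-event analysis is exploratory, is not stratified by revision type as written, and gives no day-90 risk difference. Multiple imputation is specified for pain, KOOS and PROMIS, yet no missing-outcome analysis is specified for the primary endpoint.

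**Conclusion.** The point holds. Followed as written, the ITT CMH is labelled a sensitivity analysis but does not test sensitivity to missing 90-day outcomes. On the more natural reading its difference from the like-for-like mITT result is zero by construction. On the other reading it applies one undeclared assumption that shifts the result toward the arm with more losses without a recorded SSC.

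The size is conditional. With equal loss it is small (0.0021 to 0.0024; 0.0338 to 0.0365). With 42 losses split unequally, an mITT p of about 0.05 can move to between 0.018 and 0.142. The fall from 20% to 19% or 18% is an extreme that requires every loss to precede every event. The tables and splits are assumptions; the totals, the 5%-10% loss and the SOC stratum rates come from the documents.

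The documents do not support going further and saying that the primary test is invalidated or that the trial's conclusion rests on this analysis. It is a change that should be made to a supporting analysis.

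**What to change.** In SAP 8.5.1, state that Incomplete follow-up is never scored as 'No occurrences', and replace the ITT CMH with an analysis to which all randomized subjects contribute. Either of these would serve:

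- A Kaplan-Meier day-90 risk difference with its interval, stratified by revision type. This extends SAP 8.7.6 and can use the last complication-free assessment that protocol 8.1.1 already derives.
- Multiple imputation of 90-day SSC by arm and randomized stratum, conditional on the last complication-free day, followed by the stratified test.

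Add a tipping-point analysis for informative loss. Imputation by arm and stratum alone would largely return the mITT answer.

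The cost is SAP wording and a little more programming, with no new data and a slightly wider interval for this analysis. The primary mITT test is unchanged. The change must precede final database lock, after which SAP 1 rules out amendment.

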8.6 Secondary Endpoint Analyses

Any SSI (superficial or deep) and Deep SSI will be analyzed.

8.6.1 Analysis of Subject Incidence SSI

The proportion of subjects with each value of “Occurred” or “No occurrences” or “Incomplete-Follow-up” for SSI will be summarized, as applicable, by treatment arm based on the ITT, mITT, Per Protocol and Modified Per Protocol analysis sets.

Superiority Testing

The following hypothesis will be tested for superiority:

$$\text{Null } H_0: \Delta_{\text{ciNPT-SOC}} = 0$$

$$\text{Alternative } H_a: \Delta_{\text{ciNPT-SOC}} \neq 0$$

where $\Delta_{\text{ciNPT-SOC}}$ is the difference in the proportion of subjects in the ciNPT arm with at least one SSI and the proportion of subjects in the SOC dressing arm with at least one SSI.

For the combined population, a Cochran-Mantel-Haenszel (CMH) test stratified by randomized and actual type of revision (Septic, Aseptic) will be used to compare the SSI incidence rates between two treatment arms based on the mITT analysis set. The odds ratio and its asymptotic 95% confidence interval will be computed. This test is equivalent to the test of difference for the proportions.

For the septic and aseptic subpopulations, a Chi-square or Fisher’s test, as appropriate will be performed within each actual revision type for SSI incidence rates between treatment arms based on the corresponding mITT analysis set.

Additionally, figure(s) may be generated to display the results from the analyses of this endpoint graphically.

8.6.2 Analysis of Subject Incidence Deep SSI

The proportion of subjects with each value of “Occurred” or “No occurrences” or “Incomplete-Follow-up” for deep SSI will be summarized, as applicable, by treatment arm based on the ITT, mITT, Per Protocol and Modified Per Protocol analysis sets.

The deep SSI subject incidence rates between two treatment arms based on the mITT analysis set will be compared in a similar fashion as the other endpoint described in section 8.6.1 of this document.

Additionally, figure(s) may be generated to display the results from the analyses of this endpoint graphically.

8.7 Exploratory Endpoint Analyses

In general, analyses listed below will be performed on subjects in the ITT analysis set unless otherwise specified. Analyses including revision type will be based on per actual revision type.

8.7.1 Pain Analysis

Both worst pain and average pain are measured from 0 (no pain) to 10 (pain as bad as you can imagine). A positive value of change from baseline indicates increased pain post-baseline as compared with baseline; a negative value indicates reduced pain post-baseline as compared with baseline. Both worst pain score and average pain score along with change from baseline will be summarized separately by treatment arm and by visit. Change from baseline for both worst pain score and average pain score will be analyzed separately using a mixed model, which includes (“Treatment Arm” and “Visit”) plus the interaction term (“Treatment Arm by Visit”), revision type, clinical site, and with subject as a random effect. Least squares (LS) means along with 95% confidence intervals and p-values at each post-baseline timepoint will be presented.

If an overall missing data rate for worst or average pain scores is 10% or greater, then an approach of multiple imputation based on Rubin’s [1976, 1987]^{3,4} for missing data will be used by creating several different plausible imputed data sets and appropriately combining results obtained from each of them. A basic description of the multiple imputation includes:

1. Using SAS procedures including Proc MI and Proc MIANALYZE;
2. Using the fully conditional specification (FCS) method / algorithm [Brand 1999 and van Buuren 2007]^{5,6} which is a linear regression for continuous variables;
3. Including treatment arm, age (≥ 65 or < 65 years), sex, BMI (≥ 35 kg/m² or < 35 kg/m²), race/ethnicity, material used in the TKA revision, and co-morbidities in the imputation model;
4. Creating five imputed datasets [Rubin 1996]⁷;
5. Combining completed-data estimates from five imputed datasets.

The mixed model analysis described above will be repeated based on the imputed data.

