4.12. Pain Assessment

Subjects will answer two questions asking them, on a scale from 0 (no pain) to 10 (pain as bad as you can imagine), to recall and rate their worst and average pain in the last 24

hours. Subjects will answer these questions prior to the TKA revision, at the earlier of discharge or 24 hours (\pm 2 hours) after the TKA revision, and at the weekly study treatment visits. Subjects will document whether they completed the assessment before or after consultation with the Investigator. At the weekly study treatment visits, the subject will record whether the pain assessment was performed before or after the dressing removal.

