4.3.1 Pain Assessment

- Worst pain last 24 hours
- Average pain in last 24 hours

The pain assessment consists of two self-administered questions used to evaluate the severity of a subject's pain in the past 24 hours post TKA revision.

Subjects will respond using the integer value. All efforts will be made to ensure the subject completes both pain assessments at each scheduled visit: Day 0 pre-TKA revision, Day 0 post-TKA revision and End of Treatment.

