4.3.2 Knee Injury and Osteoarthritis Outcome Subscale Score (KOOS)

The KOOS instrument is a patient-reported questionnaire to assess short-term and long-term symptoms and functions. KOOS consists of 5 subscales:

- KOOS: Knee-Related Quality of Life (QOL)
- KOOS: Sport and Recreation Function (Sport/Rec)
- KOOS: Activities of Daily Living (ADL)
- KOOS: Pain
- KOOS: Other Symptoms

The scoring details are in Section 8.7.2. All efforts will be made to ensure the subjects complete the entire assessment at each scheduled visit: Baseline (Screening or Day 0), End of Treatment, Midterm Follow-up, and Long-Term Follow-up.

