The normalized scores and change from baseline for each subscale will be summarized by treatment arm and by visit. Change from baseline for normalized scores for each subscale will be analyzed using a mixed model, which includes fixed effects (“Treatment Arm” and “Visit”) plus the interaction term (“Treatment Arm by Visit”), revision type, clinical site, and with subject as a random effect. LS means along with 95% confidence intervals and p-values at each post-baseline timepoint will be presented.

If a missing data rate for any subscale is 10% or greater, then an approach of multiple imputation based on Rubin’s [1976, 1987]^{3,4} for missing data for all subscales will be used by creating several different plausible imputed data sets and appropriately combining results obtained from each of them.

A basic description of the multiple imputation includes:

1. Using SAS procedures including Proc MI and Proc MIANALYZE;
2. Using the fully conditional specification (FCS) method / algorithm [Brand 1999 and van Buuren 2007]^{5,6} which is a linear regression for continuous variables;
3. Including treatment arm, age (≥ 65 or < 65 years), sex, BMI (≥ 35 kg/m² or < 35 kg/m²), race/ethnicity, material used in the TKA revision, and co-morbidities in the imputation model;
4. Creating five imputed datasets [Rubin 1996]⁷;
5. Combining completed-data estimates from five imputed datasets.

The mixed model analysis for each subscale described above will be repeated based on the imputed data.

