Both Global Physical Health and Global Mental Health T-Scores and their corresponding changes from baseline will be summarized separately by treatment arm and by visit. Changes from baseline for both Global Physical Health and Global Mental Health T-Scores will be analyzed separately using a mixed model, which includes (“Treatment Arm” and “Visit”) plus the interaction term (“Treatment Arm by Visit”), revision type, clinical site, and with subject as a random effect. LS means along with 95% confidence intervals and p-values at each post-baseline timepoint will be presented.

If a missing data rate for Global Physical Health or Global Mental Health is 10% or greater, then an approach of multiple imputation based on Rubin’s [1976, 1987]^{3,4} for missing data for both Global Physical Health and Global Mental Health will be used by creating several different plausible imputed data sets and appropriately combining results obtained from each of them. A basic description of the multiple imputation includes:

1. Using SAS procedures including Proc MI and Proc MIANALYZE;
2. Using the fully conditional specification (FCS) method / algorithm [Brand 1999 and van Buuren 2007]^{5,6} which is a linear regression for continuous variables;
3. Including treatment arm, age (≥ 65 or < 65 years), sex, BMI (≥ 35 kg/m² or < 35 kg/m²), race/ethnicity, material used in the TKA revision, and co-morbidities in the imputation model;
4. Creating five imputed datasets [Rubin 1996]⁷;
5. Combining completed-data estimates from five imputed datasets.

The mixed model analysis for both Global Physical Health and Global Mental Health described above will be repeated based on the imputed data.

8.7.4 30-Day Subject Incidence of SSC Analysis

The proportion of subjects with each value of “Occurred” or “No occurrences” or “Incomplete-Follow-up” for 30-Day SSC will be summarized, as applicable, by treatment arm based on the ITT, mITT analysis sets. Additionally, 30-Day SSC events by type: superficial SSI, deep SSI, dehiscence, seroma, hematoma, skin necrosis, or continued drainage will be summarized based on the mITT analysis set.

Superiority Testing

The following hypothesis will be tested for superiority:

Null H_0 : $\Delta_{\text{ciNPT-SOC}} = 0$

Alternative H_a : $\Delta_{\text{ciNPT-SOC}} \neq 0$

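### The mixed models for change in pain, KOOS and PROMIS leave out the baseline score, which gives up precision unless the true baseline slope happens to be 1

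*SAP*

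**What the plan says.** SAP 8.7 models the patient-reported scales as changes from baseline:

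- Pain (8.7.1): "Change from baseline for both worst pain score and average pain score will be analyzed separately using a mixed model".
- KOOS (8.7.2): "Change from baseline for normalized scores for each subscale will be analyzed using a mixed model".
- PROMIS (8.7.3): "Changes from baseline for both Global Physical Health and Global Mental Health T-Scores will be analyzed separately using a mixed model".

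Each section lists the same terms: treatment arm, visit, arm-by-visit, revision type, clinical site and a random effect for subject. The baseline score is in none of the lists.

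The score is available. For pain, Protocol 4.12 says "Subjects will answer these questions prior to the TKA revision", and SAP 4.3.1 gives the time points as "Day 0 pre-TKA revision, Day 0 post-TKA revision and End of Treatment". For KOOS, SAP 4.3.2 lists "Baseline (Screening or Day 0), End of Treatment, Midterm Follow-up, and Long-Term Follow-up"; SAP 4.3.3 gives the same visits for PROMIS. SAP 7.1 defines baseline as the last assessment before the revision procedure, says that it "will be used as the baseline reference for all analyses which incorporate a baseline value", and defines change as the later value minus the baseline value.

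No other section adds the covariate: not the opening of SAP 8.7, not SAP 10, and not Protocol 8.3.6, which leaves the details of these analyses to the SAP.

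**The concern.** Subtracting baseline is itself an adjustment, but one whose slope is set at 1 in advance. When the true regression of follow-up on baseline has another slope, the change score corrects by the wrong amount. It then carries avoidable noise and mishandles any chance difference in baseline between the arms. The random subject effect does not repair this, because it models correlation among a subject's change scores and does not estimate the baseline slope.

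These models are more than descriptive. Each produces least squares means, 95% confidence intervals and p-values at every post-baseline time point. That is 2 pain items × 2 time points, plus (5 KOOS subscales + 2 PROMIS scores) × 3 visits: 4 + 21 = 25 arm comparisons. SAP 1 allows planned analyses to go into regulatory submissions and manuscripts. Intervals wider than the collected data require would weaken all of that.

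**Working it through.** **What the plan gives.** The only sample-size figure is for the primary endpoint (Protocol 8.4.2, SAP 2.1). It reproduces for 20% against 10%, two-sided 0.05, 80% power: n = [1.960·√(2·0.15·0.85) + 0.8416·√(0.20·0.80 + 0.10·0.90)]² / 0.10² = (0.990 + 0.421)² / 0.01, or 199 per arm. It does not bear on this point. No SD, correlation, effect size or power is given for pain, KOOS or PROMIS, so the values below are assumptions shown as a range.

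**Variance of the arm difference at one visit.** Let the baseline SD be 1, k the follow-up SD divided by the baseline SD, and ρ the baseline-to-follow-up correlation. The true slope is ρk.

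- Change score: proportional to 1 + k² − 2ρk.
- Baseline-adjusted: proportional to k²(1 − ρ²).
- The difference between the two is (1 − ρk)², so the proportional cut is (1 − ρk)² / (1 + k² − 2ρk). It is never negative, and is zero only when ρk = 1.

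Example with ρ = 0.5, k = 1: 0.25 / 1.00 = 25.0%. Example with ρ = 0.7, k = 1.5: (1 − 1.05)² / (1 + 2.25 − 2.10) = 0.0025 / 1.15 = 0.2%.

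| ρ | k = 0.75 | k = 1 | k = 1.25 | k = 1.5 |
|---|---|---|---|---|
| 0.3 | 54.0% | 35.0% | 21.6% | 12.9% |
| 0.5 | 48.1% | 25.0% | 10.7% | 3.6% |
| 0.7 | 44.0% | 15.0% | 1.9% | 0.2% |

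At k = 1 the ratio of adjusted to change-score variance is (1 + ρ)/2 = 0.65, 0.75 and 0.85. Standard errors fall by 19.4%, 13.4% and 7.8%. Put the other way, 398 evaluable subjects under the planned models give the precision of about 259, 298 or 338 subjects with baseline added (398 × 0.65, × 0.75, × 0.85).

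**Does the planned model recover the loss by another route?** Two simulations say no.

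- A random-subject model with 199 per arm and three post-baseline visits, without site or revision type, gave model-based variance ratios of 0.649, 0.748 and 0.849, against 0.65, 0.75 and 0.85 in theory.
- The second put revision type and 15 sites in the model. All inputs were assumed: 440 subjects, site SD 0.2, revision effect 0.3, complete data, no true effect, between-follow-up correlations of 0.5, 0.6 and 0.75 for ρ = 0.3, 0.5 and 0.7, and 3,000 replicates. For the last-visit contrast at k = 1 the cuts were 33.8%, 24.3% and 14.9% with two post-baseline assessments (pain), and 34.5%, 24.7% and 13.8% with three (KOOS, PROMIS). At ρ = 0.5 the standard error fell from 0.0966 to 0.0841 and from 0.0964 to 0.0837. At ρ = 0.7, k = 1.5, adjusting cost 0.05% and 0.15% of the variance.

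**Chance imbalance.** With 440 subjects allocated 1:1, the standard error of the baseline difference is √(4/440) = 0.0953 SD, so its 95% range is ±1.96 × 0.0953 = ±0.187 SD. The change-score and adjusted estimates then differ by (1 − ρk) × 0.187. At the edge of that range with k = 1 this is 0.131, 0.093 and 0.056 SD for ρ = 0.3, 0.5 and 0.7, or 1.44, 1.13 and 0.82 adjusted standard errors (ignoring site and revision type). At ρ = 0.7, k = 1.5 it is −0.009 SD. Over repeated randomizations the difference averages to zero.

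**The case against.** The strongest reply is that this is a preference about efficiency and that the plan contains no error here. Change from baseline is a declared outcome with a defined baseline, and randomization keeps its comparison unbiased with complete data. The endpoints are exploratory, with no multiplicity adjustment, power target or decision rule, so wider intervals break no commitment. The size of the loss is unknown: the assumed range includes a case with essentially no gain. The imbalance figures describe the edge of a 95% range, and a typical imbalance would move the estimate less.

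All of that is right, and it caps the point at minor. It does not remove it. The omission is plain in all three term lists, the algebra does not depend on the unknown values, and adjustment cannot lose large-sample precision. In the no-gain case the simulated penalty was under 0.2% of the variance. The SAP already adjusts these models for revision type and site, so covariate adjustment is accepted in principle. Fixing the choice beforehand also avoids a disputed post-hoc adjustment should the arms differ at baseline.

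**Conclusion.** The concern holds, as a minor point. The three models leave out a covariate that the trial collects, and the patient-reported comparisons are less precise than they could be unless ρk is close to 1. With equal SDs and correlations of 0.3 to 0.7, the avoidable share of the variance is 35% down to 15%; over the wider SD range examined it runs from 54.0% to 0.2%. These sizes rest on assumed correlations and SD ratios and on complete data. The comparison is not biased by the omission, and neither the primary analysis nor the sample size is affected.

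**What to change.** In SAP 8.7.1, 8.7.2 and 8.7.3, add the baseline score and its interaction with visit as fixed effects. The outcome may stay as change from baseline: once baseline and baseline-by-visit are in the model, the arm contrasts are the same as for the raw score.

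The cost is two terms in each of three models. No new data or visits are needed. A subject without a baseline score already has no change score, so nobody further is excluded. SAP 1 allows changes before the final database lock if they are recorded in the document history.
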